#### **8.11.4. Visit 4 (28 to 42 Days After Visit 3): Post–Vaccination 2 Blood Draw**

- Ensure that the participant continues to be eligible for the study, and continues to comply with contraception requirements as detailed in [Section 5.3.1](#).
- Ensure that the participant continues to meet none of the withdrawal criteria as described in [Section 7.2](#) and none of the temporary delay of blood draw criteria as described in [Section 5.5](#).
- If previously provided to the participant's parent(s)/legal guardian, collect the provisioned e-diary device.
- Review the participant's e-diary data since the previous visit and follow up on any ongoing reactogenicity or use of antipyretic medication.
- Complete the Study Visit/Telephone Contact AE Checklist to:

- Inquire whether the participant had any NDCMCs since the last visit. Inquire whether the participant had any of the following related to an AE since the last visit: hospitalizations, visits to other medical facilities, medication use, or missed days of school or work. Please refer to the ISF for additional details.
- Inquire about neuroinflammatory and autoimmune conditions, such as transverse myelitis, uveitis, optic neuritis, and multiple sclerosis. Please refer to the ISF for additional details.
- Record AEs as described in the AE reporting requirements section ([Section 8.3](#)) and the [SoA](#).
- Report any SAEs to the sponsor as defined in [Section 8.3](#).
- Review AEs that were ongoing since the previous visit and record their end dates or confirm that they are still continuing.
- Record nonstudy vaccinations as described in the Concomitant Therapy section ([Section 6.5](#)).
- Record any blood transfusion (eg, whole blood, packed cells) received by the participant as described in the Concomitant Therapy section ([Section 6.5](#)).
- Record concomitant medications used to treat AEs as described in the Concomitant Therapy section ([Section 6.5](#)).
- Provide the parent(s)/legal guardian or the participant with a memory aid. Instruct the participant to use the memory aid between Visits 4 and 5 to remind him or her to review any significant illnesses, hospitalizations, NDCMCs, or visits to a medical facility with study site personnel. The memory aid is not a diary for the collection of reactogenicity. Please refer to the ISF and [Section 8.2](#) for additional details.
- Collect a blood sample (approximately 20 mL).
- Ask the parent(s)/legal guardian or the participant to contact the investigator immediately if any significant illness or hospitalization occurs.
- Schedule a telephone contact and confirm that it is scheduled within the time window per protocol.
- Complete the source documents.
- Complete the CRFs.

### **8.11.5. Visit 5 (168 to 196 Days After Last Vaccination): Telephone Contact**

- This telephone contact should occur approximately 6 months after the last vaccination (Visit 3); this contact should be attempted for all participants who have received at least 1 study vaccination, unless they have withdrawn consent.
- Contact the parent(s)/legal guardian or the participant by telephone.
- Complete the Study Visit/Telephone Contact AE Checklist to:
  - Inquire about SAEs, NDCMCs, or AEs that resulted in evaluation at a medical facility since the last visit. Please refer to the ISF for additional details.
  - Inquire about neuroinflammatory and autoimmune conditions, such as transverse myelitis, uveitis, optic neuritis, and multiple sclerosis. A checklist will be provided as a guide. Please refer to the ISF for additional details.
- Report any SAEs to the sponsor as defined in [Section 8.3](#).
- Record AEs as described in the AE reporting requirements section ([Section 8.3](#)) and the [SoA](#).
- Record concomitant medications used to treat AEs as described in the Concomitant Therapy section ([Section 6.5](#)).
- Review AEs that were ongoing since the previous visit and record their end dates or confirm that they are still continuing.
- Complete the source documents.
- Complete the CRFs.

### **8.12. Unscheduled Visits**

If the participant experiences a severe redness or swelling at the injection site (>20 caliper units), a temperature  $\geq 39.0^{\circ}\text{C}$  ( $102.1^{\circ}\text{F}$ ), or a severe headache in the 7 days after vaccination, a study site visit should be arranged as soon as possible to assess the extent of the event. The parent(s)/legal guardian or participant contact will be documented in the CRF.

If the reaction exceeds the maximum size the caliper is able to measure (>21 caliper units, [Section 8.2.1.2](#)), ensure the parent(s)/legal guardian or participant has also measured the maximum diameter of the redness and/or swelling at the injection site using the measuring tape/ruler provided.

Ask the parent(s)/legal guardian or participant to report the maximum diameter of the redness and/or swelling at the injection site daily until the reaction becomes  $\leq 20$  caliper units. Record these measurements in the CRF.

At an unscheduled visit, the participant's oral temperature should be measured and the symptom that prompted the visit should be assessed by a medically qualified member of the study staff. Findings will be recorded on the CRF. If the participant experiences any AEs, these should be recorded on the AE CRF.

If the unscheduled visit does not take place following participant report of fever  $\geq 39.0^{\circ}\text{C}$ , severe redness/swelling, or severe headache, the reason must be documented in the CRF (for example, reaction no longer present or e-diary entry error).

For the purpose of assessments performed during unscheduled visits, a medically qualified member of the study staff is a study physician or a study nurse, as applicable to the investigator's local practice.

## 9. STATISTICAL CONSIDERATIONS

Methodology for summary and statistical analyses of the data collected in this study is described here and further detailed in a SAP, which will be maintained by the sponsor. The SAP may modify what is outlined in the protocol where appropriate; however, any major modifications of the primary endpoint definitions or their analyses will also be reflected in a protocol amendment.

### 9.1. Estimands and Statistical Hypotheses

No specific hypotheses will be tested in this study.

#### 9.1.1. Estimands

The estimand(s) corresponding to each primary objective are described in the table in [Section 3](#). The estimand to evaluate the immunogenicity objective is based on the evaluable population (see [Section 9.3](#) for definition). These estimands estimate the vaccine effect in the hypothetical setting where participants follow the study schedules and protocol requirements as directed. Missing serology results will not be imputed.

In the primary safety objective evaluations, missing AE dates will be imputed according to Pfizer safety rules.

### 9.2. Sample Size Determination

The study sample size is not based on any hypothesis-testing criteria. The study aims to enroll up to 50 participants to allow for sufficient numbers when describing findings with regard to this particular population.

The probability of observing at least 1 occurrence of any AE for true event percentages between 1.0% and 5.0%, when Trumenba is administered to 50 participants, is displayed in Table 6.

**Table 6. Probability of Observing at Least 1 Event by Assumed True Event Rates**

Assumed True Event Percentage	Probability (N=50)
1.0%	0.39
1.5%	0.53
2.0%	0.64
3.2%	0.80
5.0%	0.92

In order to share the expected precision for the primary immunogenicity endpoint (proportion of participants achieving hSBA titer  $\geq$  LLOQ at 1 month after the second vaccination), the width of the exact 95% CIs is calculated for 50 participants when the proportion ranges from 0.5 to 0.9 (see Table 7).

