#### 4.1.1. Approximate Duration of Participation for Each Participant

The duration of study participation for each participant will be approximately 12 months, including a telephone contact 6 months after the last vaccination.

The study duration will be approximately 3 years. The sponsor may decide to close recruitment if enrollment of 50 participants becomes challenging after 2 years of active enrollment.

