### 9.3. Analysis Sets

For purposes of analysis, the following analysis sets are defined:

Participant Analysis Set	Description
Enrolled	All participants who sign the ICD, or whose parent(s)/legal guardian(s) sign the ICD.
Study intervention allocated	All participants who are assigned a randomization (participant identification) number in the IRT system.
Evaluable	All participants who were eligible, received all doses of the study intervention according to the vaccine schedule, had blood drawn for assay testing within the required time frames, had valid and determinate assay results for the proposed analysis, and had no major protocol deviations.

Participant Analysis Set	Description
	A major protocol deviation is one that, in the opinion of the sponsor's global medical monitor, would materially affect assessment of immunogenicity, eg, participant receipt of a prohibited vaccine or medication that might affect immune response or a medication error with suspected decrease in potency of the vaccine. Prior to the immunogenicity analysis, major protocol deviations will be identified, documented, and evaluated, using predefined protocol deviation categories and subcategories. Detailed analyses for each immunogenicity endpoint will be addressed in the SAP.
mITT	All participants who have at least 1 valid and determinate MnB assay result available at any time point from Day 1 through 1 month after the second vaccination (Visit 4 for this study).
Safety	All enrolled participants who receive at least 1 dose of the study intervention and have safety data reported after vaccination.

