#### 9.4.2. Immunogenicity Analyses

The immunogenicity data for the immunocompromised participants will be reported separately from historical data of the age-matched healthy participants. The immunogenicity will be reported in the historical age-matched controls for the time points corresponding to those for the immunocompromised participants.

Primary	
For each of the 4 primary MenB test strains, the percentage of participants with an hSBA titer <math>\geq</math> LLOQ at baseline and at 1 month after the second dose will be calculated.
 
The primary analysis for the primary MenB strains is based on the evaluable population.
 
Exact 2-sided 95% CIs for the percentages will be provided using the Clopper-Pearson method. A supportive analysis will be performed based on the mITT population. Missing serology data will not be imputed. The immunogenicity analysis will be based on observed, valid, and determinate assay results. Descriptive summaries will show the reasons for missing hSBA data for each primary strain and the percentages for each reason.

---------	---

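### Does Protocol 9.2 overstate the precision of the primary immunogenicity endpoint by calculating Table 7 for the full 50 participants?

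*Protocol*

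**What the plan says.** Protocol 9.2 (Sample Size Determination) sets the size as a ceiling and without a hypothesis test: "The study aims to enroll up to 50 participants to allow for sufficient numbers when describing findings". It then gives two tables. Table 6 shows the chance of seeing at least one adverse event "when Trumenba is administered to 50 participants, is displayed in Table 6". Table 7 is introduced by "In order to share the expected precision for the primary immunogenicity endpoint", and the same sentence goes on to say that "the width of the exact 95% CIs is calculated for 50 participants when the proportion ranges from 0.5 to 0.9". The Table 7 column header repeats N=50.

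Three other places bear on the denominator:

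- Protocol 4.1.1 allows a smaller study: "The sponsor may decide to close recruitment if enrollment of 50 participants becomes challenging after 2 years of active enrollment".
- Protocol 9.1.1 says "The estimand to evaluate the immunogenicity objective is based on the evaluable population", and Protocol 9.4.2 confirms that "The primary analysis for the primary MenB strains is based on the evaluable population".
- Protocol 9.3 restricts that set to eligible participants dosed and bled on schedule who "had valid and determinate assay results for the proposed analysis, and had no major protocol deviations". Missing serology is not imputed.

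The SAP adds that insufficient, indeterminate and not-done assay results count as missing (5.3.2). It reports the numerator, denominator, percentage and exact interval separately for each strain (6.1.1.1.1).

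**The concern.** The study is one of estimation, so interval width is the only quantitative support that 9.2 gives for the sample size on the primary immunogenicity endpoint. A reader who takes *expected* literally would assume that the report will show intervals of about the Table 7 width. The denominator for a strain reaches 50 only if enrolment is full, nobody is lost or excluded, and every Visit 4 sample gives a determinate result for that strain. It cannot exceed 50. At each assumed proportion, the table therefore shows the narrowest width that the enrolment cap allows, and 9.2 gives no case with a smaller N. If the final evaluable count fell well short, the planned precision would look optimistic.

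**Working it through.** **Inputs.** N=50 and proportions 0.5 to 0.9 (Protocol 9.2, Table 7); two-sided 95% Clopper-Pearson intervals (Protocol 9.4.2). The documents give no evaluable rate, so every N below 50 is an assumption.

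**Formula.** With x responders among N:

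- lower limit = 2.5% quantile of Beta(x, N − x + 1)
- upper limit = 97.5% quantile of Beta(x + 1, N − x)
- width = upper − lower

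**Step 1: the plan's own figures.** At N=50, x = 25, 30, 35, 40 and 45. For x = 40 the limits are 0.6628 and 0.8997, so the width is 0.8997 − 0.6628 = 0.2369. The five widths are 0.2895 (0.28945 before rounding), 0.2841, 0.2675 (0.26746), 0.2369 and 0.1849. Table 7 states 0.289, 0.284, 0.267, 0.237 and 0.185, so all five agree.

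**Step 2: smaller assumed N.** N=40 and N=30 give whole responder counts at every listed proportion, so these are widths the trial could actually report.

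| Proportion | N=50 | N=40 | Ratio 40/50 | N=30 | Ratio 30/50 |
|---|---|---|---|---|---|
| 0.5 | 0.2895 | 0.3240 | 1.12 | 0.3741 | 1.29 |
| 0.6 | 0.2841 | 0.3181 | 1.12 | 0.3674 | 1.29 |
| 0.7 | 0.2675 | 0.2997 | 1.12 | 0.3466 | 1.30 |
| 0.8 | 0.2369 | 0.2660 | 1.12 | 0.3085 | 1.30 |
| 0.9 | 0.1849 | 0.2087 | 1.13 | 0.2442 | 1.32 |

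At N=45, the proportions 0.6 and 0.8 give whole counts (27 and 36). Their widths are 0.2997 and 0.2502, each about 6% above N=50.

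**Step 3: size on the reported scale.** From N=50 to N=40 the added width runs from 0.2087 − 0.1849 = 0.0238 to 0.3240 − 0.2895 = 0.0345. Halved, that is 1.2 to 1.7 percentage points per side on average. At 80% response the interval is 66.3% to 90.0% for 40/50, 65.4% to 90.4% for 36/45, and 64.4% to 90.9% for 32/40.

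**Step 4: how far *best case* holds.** It holds only at a fixed proportion. At 38/40 (95%) the width is 0.163, below the smallest Table 7 entry of 0.185. Nor is *expected* used in its technical sense. Averaging the width over the binomial distribution of x at N=50 gives 0.2868, 0.2814, 0.2645, 0.2335 and 0.1805, slightly narrower than the table. Table 7 shows the width when the observed proportion equals the assumed one at N=50, which is ordinary planning shorthand.

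**The case for a change.** The strongest case for acting is that the N=50 label states which N was used but does not say that this N is a maximum, or that the analysis set is drawn from a smaller group. The documents themselves provide for losses: dosing and blood-draw windows, prohibited medications, major deviations, indeterminate assays, and permission to stop recruitment early. The SAP's evaluable immunogenicity population (Section 4) requires only one determinate result after Vaccination 2, so a single strain's denominator can fall below even the evaluable count. Full enrolment with no loss is therefore the limiting case, and *expected* is not the exact word for it. That much stands.

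It does not amount to a reason to change the plan. The condition is stated in the same sentence and in the column header, the enrolment ceiling appears at the start of the same section, and the evaluable definition comes directly after the table. Adding columns at N=45 or 42 would mean choosing sample sizes that no document supports, and several entries would need fractional responder counts (40.5 of 45, for example). Table 6 needs no relabelling either, because its text already conditions on 50 vaccinated participants and makes no claim about what is expected.

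**Conclusion.** No change follows, because there is nothing to gain. Table 7 is correct for the N it states, and that N is in plain view. *Expected* is loose by an amount that depends on the final count: about 6% in width at an assumed N=45, 12% to 13% at 40, and 29% to 32% at 30. None of these counts is a forecast.

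No hypothesis is tested (Protocol 9.1), no target width is set, and no analysis or enrolment decision refers to the table. Because the SAP reports the achieved numerator, denominator and exact interval for each strain, readers of the results will see the true precision whatever 9.2 calls the planning figure. The conclusion rests on the study remaining descriptive. If a precision target or a comparison were ever attached to the primary endpoint, the gap between the ceiling and the evaluable count would matter.

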**Table 7. Width of 95% Exact Confidence Interval by Response Rate**

Assumed Proportion	Width of Exact 95% Confidence Interval (N=50)
0.5	0.289
0.6	0.284
0.7	0.267
0.8	0.237
0.9	0.185

### 9.3. Analysis Sets

For purposes of analysis, the following analysis sets are defined:

Participant Analysis Set	Description
Enrolled	All participants who sign the ICD, or whose parent(s)/legal guardian(s) sign the ICD.
Study intervention allocated	All participants who are assigned a randomization (participant identification) number in the IRT system.
Evaluable	All participants who were eligible, received all doses of the study intervention according to the vaccine schedule, had blood drawn for assay testing within the required time frames, had valid and determinate assay results for the proposed analysis, and had no major protocol deviations.

Participant Analysis Set	Description
	A major protocol deviation is one that, in the opinion of the sponsor's global medical monitor, would materially affect assessment of immunogenicity, eg, participant receipt of a prohibited vaccine or medication that might affect immune response or a medication error with suspected decrease in potency of the vaccine. Prior to the immunogenicity analysis, major protocol deviations will be identified, documented, and evaluated, using predefined protocol deviation categories and subcategories. Detailed analyses for each immunogenicity endpoint will be addressed in the SAP.
mITT	All participants who have at least 1 valid and determinate MnB assay result available at any time point from Day 1 through 1 month after the second vaccination (Visit 4 for this study).
Safety	All enrolled participants who receive at least 1 dose of the study intervention and have safety data reported after vaccination.

## 9.4. Statistical Analyses

The SAP will be developed and finalized before any analyses are performed and will describe the analyses and procedures for accounting for missing, unused, and spurious data. This section is a summary of the planned statistical analyses of the primary objectives.

### 9.4.1. Historical Age-Matched Healthy Controls

Historical data from age-matched healthy participants from Study B1971057, a pivotal Phase 3 MnB study that has previously completed the primary analysis, will be used as a reference for safety and immunogenicity of Trumenba. Healthy adolescents and young adults (10 to <26 years of age) from B1971057 will be randomly selected and a historical age-matched healthy control group will be used to provide context and assist with the interpretation of the immunogenicity and safety data for the immunocompromised participants. The safety and immunogenicity data will be reported separately for the immunocompromised and healthy control participants. The selection of the participants for the historical age-matched controls is based on 1 previously completed Phase 3 MnB study, B1971057 (Stage 1). Study B1971057 followed the same 0- and 6-month dosing schedule and used the same methodology for assessment of immunogenicity and safety as in this study. Healthy adolescents and young adults (10 to <26 years of age) were enrolled in B1971057 and the immunopersistence stage of the study (Stage 2) is ongoing. The same age distribution will be ensured for both the healthy controls and the immunocompromised participants by randomly selecting age-matched healthy participants from Study B1971057

who were randomized to Trumenba. For immunocompromised participants 10 to <26 years of age in this study, age-matched control participants will be randomly selected from Study B1971057. For immunocompromised participants older than 25 years of age in this study, the controls will be randomly selected from participants 25 years of age from Study B1971057. No participants will be randomly selected as control more than once. For Study B1971057, only participants randomized to Group 2 or Group 4 (Trumenba groups) will be eligible to be selected as healthy controls. Further details will be available in the SAP.

#### 9.4.2. Immunogenicity Analyses

The immunogenicity data for the immunocompromised participants will be reported separately from historical data of the age-matched healthy participants. The immunogenicity will be reported in the historical age-matched controls for the time points corresponding to those for the immunocompromised participants.

Primary	
For each of the 4 primary MenB test strains, the percentage of participants with an hSBA titer <math>\geq</math> LLOQ at baseline and at 1 month after the second dose will be calculated.
 
The primary analysis for the primary MenB strains is based on the evaluable population.
 
Exact 2-sided 95% CIs for the percentages will be provided using the Clopper-Pearson method. A supportive analysis will be performed based on the mITT population. Missing serology data will not be imputed. The immunogenicity analysis will be based on observed, valid, and determinate assay results. Descriptive summaries will show the reasons for missing hSBA data for each primary strain and the percentages for each reason.

---------	---

#### 9.4.3. Safety Analyses

All safety analyses will be performed on the safety population. Separate safety populations will be defined for each vaccination visit and follow-up phase and will be detailed in the SAP. The safety data for the immunocompromised participants will be reported separately from the historical data of the age-matched healthy participants. The safety will be reported in the historical age-matched controls for corresponding analysis intervals to those for the immunocompromised participants.

Endpoint	Statistical Analysis Methods
Primary	The proportion of participants reporting local reactions at the study intervention administration site and systemic events within the 7-day period after each vaccination will be descriptively summarized.

Endpoint	Statistical Analysis Methods
	
Two- sided 95% CIs based on the Clopper Pearson method will be presented with the proportions. Severities of local reactions and systemic events reported after each vaccination will also be descriptively summarized.
 
The proportion of participants reporting the use of antipyretic medication for Days 1 through 7 will be summarized after each vaccination.
 
The percentage of participants reporting at least 1 SAE, the percentage of participants reporting at least 1 MAE, and the percentage of participants reporting at least 1 NDCMC will be descriptively summarized (percentages and associated Clopper-Pearson 95% CIs) for each time period defined in Section 3.
 
All AEs and SAEs will be categorized according to the latest version of MedDRA. An MAE is defined as a nonserious AE that results in an evaluation at a medical facility. An NDCMC is defined as a disease or medical condition not previously identified that is expected to be persistent or otherwise long-lasting in its effects. AEs, SAEs, MAEs, and NDCMCs will be summarized.
 
Missing AE dates will be handled according to the Pfizer safety rules.
 
Detailed analyses for each safety endpoint will be addressed in the SAP.

